3.0 Intervention to be studied

The intervention is a multicomponent (3-part) technology-based package. The intervention targets influences and processes informed by the Pediatric Self-Management framework (Table 1). Component 1 (education) consists of continuous access to directed educational resources on the SCD process, treatment, home management strategies, symptom prevention and management strategies. These materials are easily accessible via a mobile device given to caregivers and children (8-17 years) and will include patient-centered PDF files and links to websites developed and tested by authoritative sources. An example includes the patient education materials provided by NIH NHLBI such as the Sickle Cell Disease Infographic: Monitoring Pain (Figure 1). To address potential literacy barriers, an

application that reads PDF files aloud (e.g. @Voice Aloud Reader) is downloaded onto devices. Component 2 (symptom monitoring and tracking) consists of a mobile-device based publicly available application for tracking and monitoring pain in SCD that also permits upload of symptom logs and text alerts to a health care provider (Voice Crisis Alert). Component 3 (caregiver-provider communication) is based on Jacob et al. (2013)'s intervention with an mHealth intervention for older children with SCD. This component consists of a technology-based connection with a provider who will: respond to alerts delivered via the mHealth application, monitor pain symptoms delivered via the mHealth application, and respond to messages. A provider at the MUSC Pediatric Sickle Cell Clinic will collaborate with caregivers to coach caregivers on the care of the child and provide support to the caregiver.¹⁰ Caregivers will receive a daily message using a semi-structured protocol to "check in" with participants and promote engagement. All components are integrated into the web-based app. A secure portal is in place for messaging that encrypts all messages and protects confidentiality.

Children (8-17) with SCD and their caregivers will complete self-report and proxy assessments as described in Table 1 below; data will be recorded in REDCap by the PI or project coordinator

Major tasks and domains	Measures/instruments/questions and Cronbach's alpha ()	Data sources and time points

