Demographics/clinical characteristics	Age, child age, health history, race/ethnicity, medications, health care utilization, rural/urban residence, insurance, caregiver demographics, family characteristics	Caregiver interview; baseline
Reach: Sample Recruitment	Monitoring of sample representativeness; types of recruitment activities; rates of recruitment; % eligible, consented, provided with informational session	Recruitment tracking forms; quality checks by PI; weekly meetings with mentor, clinic staff, and research team
Efficacy: Child (by proxy): Pain Fatigue Quality of life Caregiver: Fatigue Emotional distress: anxiety Emotional distress: depressive symptoms Measures of self-management behaviors: Monitoring and tracking symptoms Attending clinic appointments Administering home medications and treatments	PROMIS Parent Proxy: Pain Interference* ^{21,22} (age 5 and older) Self-efficacy SEMCD-6 PedsQL with Sickle Cell Disease Module (proxy = 0.97) ²³ (age 2 and older) PedsQL Multidimensional Fatigue Scale in Sickle Cell Disease (proxy = 0.95) ²⁴ (age 2 and older), PROMIS Fatigue SF, Depression SF (>0.9) ²⁵ PROMIS Emotional Distress: Anxiety (0.97) ²⁶ PROMIS Emotional Distress: Depressive symptoms SF (0.97) ²⁷ Daily pain severity rating; daily pain type rating # days recorded symptoms; # days and types of recorded treatments; # scheduled clinic appointments attended; # days daily mediation administered; # days PRN medications administered	Review and content analysis of transcriptions of text messages; review and content analysis of recorded teleconferences; tracking forms; fidelity checklist; transmissions from web-based application to nurse; post-intervention interviews; weekly meeting with mentor, clinic staff, and research team; baseline, mid-intervention, post-intervention, 3-months post-intervention

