Adoption: Adherence Acceptability Education	# days symptoms recorded; # times educational component accessed; length of time in minutes educational component accessed; # text messages and videoconferences with nurse Caregiver satisfaction; # problems reported; types of problems reported # times accessed educational materials; length of time in minutes educational materials accessed # days recorded symptoms; # contacts (text or videoconferencing) with nurse pertaining to symptoms	Tracking forms; content analysis from text messages and videoconferences with nurse, data transmitted from web-based application; fidelity checklist; weekly meetings with mentor and research team; caregiver interview at end of study

Symptom monitoring and tracking	# and type (screening, referring, coaching, supporting) of contacts (text or videoconferencing) with nurse	
Patient-provider communication	Collaborate for Parents	
Implementation: Technology	# problems encountered with mobile device, # problems reported to research staff; types of problems reported	Tracking forms; weekly meeting with mentor and research team; caregiver interview at end of study
Consistency of intervention	instructional session conducted as planned; fidelity to protocol maintained MAPS	
Maintenance: Projection of future adoption	# caregivers who would continue intervention; caregiver perception of the intervention; feasibility of nurse role	Caregiver interview at end of study; weekly meetings with mentor, clinic staff, and team

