10.0 Study Design / Methods

The mHealth SCD management intervention will be delivered via an app on both the caregiver and child mobile devices over a 12-week period. This multi-component, web-based app consists of 1.) continuous access to directed educational resources on the SCD process, treatment, home management strategies, symptom prevention and management strategies; 2.) a series of pages in the app that allow for tracking and monitoring symptoms; and 3.) child/caregiver – provider communication. The educational component is based on patient-centered materials that have been developed and tested by authoritative sources. In the app, educational materials are organized by user age (for individuals with SCD) or role for parents/caregivers. Citations are provided and links to the sources are included. The symptom tracking and monitoring component consists of a customizable avatar on which the user can record the location, severity, and characteristics of pain. Users can record other concurrent or associated symptoms (such as fatigue) and can view a graph

with the pain history. This portion of the app also includes a health history page on which users can document important clinical information, such as sickle cell type, last sickle cell crisis hospitalization, medications, and allergies. The child/caregiver – provider communication component consists of the ability for the child/caregiver to send a secure message to providers within the app to communicate pain and other symptoms. Providers will have the capability to securely send a reply within the app. In addition, children/caregivers can choose to receive a daily “support” message that will be automatically sent from a list of possible messages. All communication is encrypted and sent securely within the app via a portal. Two to three providers at the MUSC Sickle Cell Clinic will participate as the designated providers in the study.

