To determine feasibility, we will apply the RE-AIM framework to assess the Reach, Efficacy, Adoption, Implementation, and Maintenance of the intervention with 30 children/caregiver dyads.¹⁸ The domains are further explicated in Table 1. The intervention will be loaded onto the child’s and caregiver’s tablet or smartphone (Apple or Android); participants without a device will be provided one for the duration of the study. The PI or PC will deliver detailed verbal instructions to the participants on the use of the device and the intervention. Participants will also receive written instructions and a contact number for technical assistance if needed. Baseline measures (Table 1) will be collected during the same meeting. Participants will retain the devices and will participate in the intervention over a 12 week-period. At the end of the 12-week period, the PI will conduct a post-intervention meeting with each individual caregiver and child participant during which post-intervention data collected. Caregivers will also be asked to return the mobile device at the end of the study. The PI will meet with the study provider weekly during the intervention.

Retention: To improve retention, IRB-approved personnel will contact enrolled participants at 3-week intervals between data collection points. The timeline for these points of contact are at the following weeks post baseline data collection: weeks 3, 9, 15, 18, and 21. The purpose is to maintain contact with enrolled participants, not data collection. Correspondence will be logged in REDCap. Contact will take place via text message, using the number(s) provided to study personnel upon enrollment. Examples of messages are provided in an uploaded attachment.

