12.0 Data Management

Sample size considerations

The purpose of this study is to establish feasibility of implementing the integrated intervention obtain estimates of variability for the primary outcome measures and obtain preliminary indicators of effectiveness of the intervention rather than to confirm or refute hypotheses. Therefore, sample size considerations focus on precision of estimates. For this feasibility study, we project that we will be able to recruit 30 child/caregiver dyads. With such a sample we will be able to estimate outcome proportions for feasibility measures including recruitment and drop-out with precision ± 0.11 to ± 0.16 for values of the true proportion ranging from 0.10 to 0.30 (or correspondingly, from 0.70 to 0.90). Assuming a drop-out rate of up to 30%, 95% confidence limits can be estimated for impact measures, such as change from pre-to-post in quality of life for child and caregiver with a precision ranging from ± 0.43 to ± 1.35 corresponding to estimated standard deviations for change in quality of life scores ranging from 0.5 to 5.0 SD units.

Demographic and clinical variables obtained at baseline will be described via measures of central tendency (mean, median), variability and frequency distributions as appropriate. Additionally, demographic and clinical characteristics for those who adhered to the study protocol (study completers) versus those who did not adhere (non-adherers and drop-outs) will be compared to better describe the population for this study. For continuous quality of life measures for the child and caregiver the difference between pre and post intervention measurements will be estimated via 95% confidence intervals. To assess preliminary intervention effects, we will conduct repeated measures ANCOVA with symptom (pain) severity and type obtained daily as dependent variable in individual models adjusting for “dose” defined as number of times education module was accessed and total time spent in education modules.

Post-intervention qualitative analyses (Aim 2): Data collected from post-intervention key informant interviews will be analyzed using directed content analysis¹⁹ and nVivo qualitative data analysis software version 11.²⁰ Consistent with the directed content analysis approach, initial coding categories are identified according to the guiding theoretical model, and for this study, will reflect the RE-AIM domains.

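### The daily-pain ANCOVA adjusted for education dose cannot estimate an intervention effect; it gives an uncontrolled trend or a dose association and should be labelled as such

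*Combined protocol and SAP*

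**What the plan says.** Section 12.0 of the 8-17 years protocol assigns the assessment of preliminary effects to a "repeated measures ANCOVA with symptom (pain) severity and type obtained daily as dependent variable in individual models adjusting for" dose, defined as the "number of times education module was accessed and total time spent in education modules". Section 12.0 of the 0-7 years protocol has the same text. No other statistical model appears in either protocol. The other quantitative efficacy analysis is a pre/post difference in quality of life with a 95% CI.

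Related text:

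- **Design (10.0).** All 30 dyads per protocol receive the app for 12 weeks. The only random selection is of 15 dyads for interviews. The app is explained and baseline is taken at one visit: "Baseline measures (Table 1) will be collected during the same meeting".
- **Outcome (3.0 measures table; 10.0).** The table lists "Daily pain severity rating; daily pain type rating" without a scale for type. In the app the user "can record the location, severity, and characteristics of pain".
- **Adherence (3.0 measures table, Adoption row).** The measures include "days symptoms recorded; # times educational component accessed".
- **Scheduled pain measure (3.0 measures table, Efficacy row).** PROMIS Parent Proxy Pain Interference, for age 5 and older, is listed at baseline, mid-intervention, post-intervention and 3 months later. Section 12.0 does not name an analysis for it.
- **Purpose (12.0).** The study seeks "preliminary indicators of effectiveness of the intervention rather than to confirm or refute hypotheses".

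**The concern.** An intervention effect needs a contrast: treated against untreated families, or at least the period on the app against a period before it. The daily series offers neither, since every family is treated and the series starts with the app.

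Adjusting for dose does not supply the contrast. Dose is measured after baseline, is chosen by the family, and reflects only the education component, not symptom tracking or provider communication. Families may open the education pages because the child is in pain, so a dose coefficient is open to confounding by pain itself.

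At stake is the pain part of the secondary aim. A background change in pain, or a difference in who opens the modules, could be carried into the next study as a signal of efficacy. Meanwhile the pain instrument that has a true baseline has no explicitly named analysis.

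**Working it through.** The plan gives no sample size, power or precision for this model, so there is no figure to reproduce. The check is structural. The numbers below are illustrations on assumed inputs, because the documents give no pain scale, pain frequency or logging rate. The plan names no test; the rejection rates use 5% tests added here.

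**1. What the model can estimate.** With one treated group and no daily series before the app, two kinds of term remain: time on treatment and education use.

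*Time.* Assume no intervention effect, 30 dyads, 84 days, independent daily errors with SD 1.5, and the same trend in every dyad. Suppose pain falls by 0.5 points over 12 weeks for other reasons. With time scaled 0 to 1, its sum of squares per dyad is 84 x 85 / (12 x 83) = 7.17. The SE of the mean slope is 1.5 / sqrt(30 x 7.17) = 0.102, and 0.5 / 0.102 = 4.9. In 400 simulated studies the trend was significant in over 99%, against 6% with no background fall.

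*Dose.* Under the same assumptions, with between-dyad SD 1.5, suppose a dyad's usual pain correlates 0.3 or 0.5 with its education use. The dose coefficient was significant in about 35% or 82% of runs, with no intervention effect present.

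**2. What the dose adjustment does to the trend.** This depends on the period over which dose is counted, which is not stated.

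- *12-week total.* This is constant within a dyad, so it shifts dyad levels and barely touches the within-dyad slope. Assume education truly lowers mean severity from about 1.2 to 0.75 (300 runs, 30 dyads, two levels of spread in use between families). A fall was found in 81.3% and 80.0% unadjusted, and in 81.7% and 80.0% adjusted.
- *Running total.* This rises with time and carries the education pathway, so adjustment removes that part of the trend. With use counted to the previous day, a fall was found in 2.3% and 3.7%. With half the true effect, the unadjusted model itself found it in only 38.0% and 32.7%.

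The phrase about total time makes the 12-week total the likelier reading.

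**3. Unlogged days.** Days with symptoms recorded is an adherence measure, so gaps are expected, and no rule for them is given. Let p be the share of pain days, qp and qf the logging rates on pain and pain-free days, 5 the mean severity on pain days, and s0 the score for no pain:

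logged mean = (5·p·qp + s0·(1-p)·qf) / (p·qp + (1-p)·qf); true mean = 5p + s0·(1-p).

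Take p = 0.25 and s0 = 0, so the true mean is 1.25.

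- Pain-free logging falls from 70% to 50%: 0.875 / 0.550 = 1.591, a shift of +27%.
- Pain-day logging falls from 70% to 50%: 0.625 / 0.650 = 0.962, a shift of -23%.
- With s0 = 1 the shifts are +14% and -12%.
- A fall only to 60% gives +12% and -11% (s0 = 0), or +6% and -6% (s0 = 1).
- If both rates fall alike the shift is nil. If only pain days are entered, this mechanism cannot arise.

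In simulation, removing total dose from the model changed no false-trend rate by more than 0.6 percentage points. The bias therefore belongs to the daily series, not to this ANCOVA.

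**4. Pain type.** Listing type apart from severity, and recording pain characteristics in the app, suggest categories. If so, the mean of the codes, and any ANCOVA on it, changes when the categories are renumbered. If type is a numeric rating, this objection falls away.

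**5. Precision of the scheduled alternative.** The 95% half-width in SDs of change is t(n-1) / sqrt(n).

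- n = 30: 2.045 / 5.477 = 0.37.
- n = 21 (30% drop-out): 2.086 / 4.583 = 0.46.
- In the 0-7 study, ages 5-7 are 3 of 8 one-year bands. If ages are evenly spread (assumed), 30 x 3/8 is about 11 dyads, and 21 x 3/8 about 8.
- n = 11: 2.228 / 3.317 = 0.67. n = 8: 2.365 / 2.828 = 0.84.

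**The case against.** The strongest reply is that this is a feasibility study that disclaims hypothesis testing, so loose wording about effects does little harm. That limits the reach but does not remove the point: signals of efficacy are a stated aim, and estimating without testing does not change what the estimate measures.

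Several stronger readings are tempting, and the documents do not support them.

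- *The adjustment hides a real benefit.* This needs a running total, which the plan does not state.
- *The plan will report the dose coefficient as an effect.* It lists dose only as an adjustment. The confounding figures show what would follow if the coefficient were so read.
- *Biased logging is a fault of this model.* It would affect any model of the daily series, including the replacement below. The daily message ("Caregivers will receive a daily message using a semi-structured protocol" in section 3.0, optional in section 10.0) and the weekly contact in section 13.0 may limit it.
- *ANCOVA is wrong for pain type.* That holds only if type is categorical.
- *The PedsQL sickle cell module can serve as the pain measure for ages 2-4.* The documents do not say that it measures pain.

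It is also fair that the scheduled pre/post change is itself uncontrolled, measures interference rather than severity, and covers a minority of the 0-7 sample. Its advantage is a true baseline at fixed visits.

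**Conclusion.** The point holds and is worth correcting before analysis. In both protocols the model assigned to preliminary effects can estimate only an on-treatment trend or an association with self-selected education use. This follows from the design and does not rest on any simulated figure.

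The remaining parts are conditional: loss of a benefit that works through education, on a running total; dependence on arbitrary codes, on a categorical pain type; a logging artefact, on pain-dependent logging with pain-free days entered.

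The reach is the daily-pain part of the secondary aim. Feasibility and the quality-of-life intervals are not affected. The size of any false signal cannot be derived from the documents.

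**What to change.** Amend section 12.0 in both protocols:

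1. **Main pain signal.** Use the baseline-to-12-week change in PROMIS Parent Proxy Pain Interference (age 5 and older) with a 95% CI, stated to be uncontrolled. Say that no scheduled pain instrument is named for children under 5, so in the 0-7 study the daily trend is the only description of pain at those ages.
2. **Daily severity.** Fit a linear mixed model to all logged days, with week as a fixed effect, dyad random intercept and slope, and serially correlated errors, not adjusted for dose. Drop the random slope if the model does not converge; on assumed data with 21 or 30 dyads it converged in 799 of 800 runs. Call the result a descriptive within-group trend. Report weekly logging rates beside it, say whether and how pain-free days are scored, and state that bias from pain-dependent logging remains.
3. **Education use.** Report it only as an exploratory association, using use up to the previous day, and neither as an intervention effect nor as an adjustment. Say that comparisons between families stay confounded.
4. **Pain type.** Define its scale. If categorical, use a binary or categorical GEE or mixed model, or weekly proportions with dyad-clustered 95% CIs.

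The cost is analysis wording and some programming, with no new data or visits. The daily-pain and dose results become explicitly descriptive, and the pain-interference interval in the 0-7 study is wide.

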13.0 Provisions to Monitor the Data and Ensure the Safety of Subjects

There is a well-developed and NIH/NINR prepared SRG approved DSMP that involves the use of a Safety Monitoring Committee (SMC) that shall meet semi-annually post initial study enrollment. The Committee is comprised of key individuals that include: an independent medical safety monitor (ISM), a biostatistician (BS), and the Program Manager (PM).

The following members of the study’s DSMC will perform data safety monitoring of the study:

- [name], Independent Safety Monitor (ISM) - primary responsibility
- [name], MS, Project Manager (PM)
- [name], Biostatistician (BS) - supervised by [name].

Independent Safety Monitor (ISM), [name] who is Assistant Professor at Medical University of South Carolina, has a PhD and a background as a clinical psychologist with expertise in adolescent behavioral research, and will act as the study’s Independent Safety Monitor (ISM). [name] has no real or apparent conflict of interest that would affect her performance in this role on the study.

Project Manager, (PM). [name], MS, has over 20 years of research experience in study management, quality assurance and the protection of human subjects. [name] is CTRC, CITI /GCP and NIH trained in Human Subject Protections, and has completed MUSC's Certificate of Competence in Research Ethics (CREP) and member of the Institute of Human Values Ethics Committee. [name] has also been a member of over 5 federally and FDA sponsored research full DSMBs.

Biostatistician (BS) [name] is a biostatistician and faculty at the College of Nursing at the Medical University of South Carolina. [name] has experience collaborating with investigators in clinical trials as well as in community based participatory research. [name] will be supervised by [name] from the College of Nursing.

From the initial screening of subject by inclusion and exclusion criteria to the informed consent process to the provision of participant study instruction to staff training in Good Clinical Practices (GCP) and regulations pertaining to the Conduct of Human Subject Research to routine contact with participants to internal quality control audits and protocol fidelity monitoring to the real-time review of AE's by the SMC to the oversight of the IRB - procedures for monitoring study safety are consistently afforded throughout the study. Specific study procedures include:

- Participants will be screened for inclusion and exclusion per the protocol
- Participants will be fully informed as to all known risks and the possibility of risk from study participation in the informed consent process. These risks are minimal.
- Participants will be instructed to notify the researchers of any/all suspected or experienced adverse events whether they believe them to be related or not to the intervention.
- The PI or PC will track all reported participant AEs through to resolution.
- All investigators and researchers will maintain active CITI and GCP training.
- The PI or PC will maintain weekly contact with all participants to elicit information about AE's and to monitor participant study progress, compliance and safety.
- The PI or PC will review participants study logs for fidelity compliance with the intervention.
- The PI or PM will conduct quarterly internal quality control audit of all participant records to ensure compliance with MUSC IRB regulations; the PI and PC will work together to correct any errors.
- The BS shall generate semi-annual AE reports for the PI, SMC and IRB to review.
- The ISM will have access to real-time study data and will be able to provide immediate recommendations to the PI and PD.
- Investigator performance and compliance will be provided for through MUSC IRB and ORI study oversight.

Protecting Confidentiality of Participant Data

Participant Screening and Enrollment. All data from participants screened for the study will be entered into an electronic study database. Designated research staff will collect, gather, and enter required data (written informed consent, HIPAA Authorization, and demographics) onto study data forms. Screened patients who do not meet study eligibility will have specific screening data entered into the study database. The collected data will be helpful in examining the patient population and feasibility of enrollment criteria and will include reason for exclusion. All dates will be shifted and other Personal Health Information (PHI) will be removed from the study database upon study completion. All data obtained from this study will be used for research purposes only and will comply with Federal HIPAA regulations. Master Screening and Enrollment Logs will be maintained by the PI or PD and will be used by the PI or PD to prepare reports on accrual and attrition for the ISM and SMC.

Case Report Forms. All proposed study specific case report forms (source documents) for data collection will be designed by the PI and, when possible, transferred by the PI or PC into electronic Case Report Forms (eCRFs) for use in the study's REDCap database. These study specific eCRFs source documents (study logs for correspondence, compensation and other forms such as pre-eligibility screens) will be coded by the participant's unique study ID# for all data collected including study instruments will be maintained in the participant research record. Completed instruments that require signature on a paper CRF will be scanned and uploaded into the study database to all for remote electronic safety monitoring as well as maintained on file in accordance with MUSC policies and applicable Federal Regulations for the Conduct of Human Participant Research.

Binders. The PI or PC will prepare and maintain a participant-specific binder for each participant containing all non-eCRFs records. A regulatory file will also be maintained to include the IRB-approved Protocol, original Informed Consent documents, HIPAA forms and other study-related regulatory documents. All paper research records and CRFs will be maintained in a locked file cabinet, stored in a room for research files that is accessible only via a password protected entry system that features security cameras, within the College of Nursing. Access to the research records, study database and PHI's will be restricted to study personnel as approved by the PI and MUSC IRB. As with all studies conducted at MUSC, this study is also eligible for a random audit by MUSC Office of Compliance.

Data Processing. This study will use Research Electronic Data Capture (REDCap) for data capture and management. REDCap is a software toolset and workflow methodology for the electronic collection and management of research and clinical trials data. REDCap provides secure, web-based, flexible applications, including real-time validation rules with automated data type and range checks at the time of data entry. Exports are made available for several statistical packages including SPSS, SAS, SATA, R and Microsoft Excel. The study-specific REDCap electronic database will be designed and developed by the PI or PD in concert with the BS. The provision of REDCap is made available through the South Carolina Clinical & Translational Research (SCTR) Institute at MUSC with NIH Grant awards UL1RR029882 and UL1TR000062.

Data Security. Ensuring data security, compliance with 45 CFR 46 and maintaining the integrity of PHI is a top priority. MUSC has Standard Operating Procedures (SOP) to ensure a high level of data security while coordinating electronic and paper data management activities for clinical research trials. The REDCap study database will be hosted in the Biomedical Informatics secure data center at MUSC, a secure environment for data systems and servers on campus, and includes firewall, redundancy, failover capability, backups and extensive security checks. The secure data center has strict access control; only authorized core personnel may access the facility un-escorted. Only authorized users are allowed to connect to the network, and the security of the network is actively monitored. Power and environmental controls have several layers of backups, from interruptible power supplies to alternate and redundant feeds to the local utility company. The REDCap system administrator contributes to the maintenance of institutional disaster recovery and business continuity plans. Load balancers and a highly fault tolerant SAN infrastructure contribute to high availability.

The REDCap system itself has several additional layers of protection including password protection. Access to the data and its security is managed institutionally by sponsored login IDs through a Shibboleth login with an MUSC issued NetID and features a user account management filter that controls who can access the data and to what degree. All personnel must pass an employment background check before being issued an ID. Password complexity, history and expiration standards are implemented at the institutional level. Access to individual REDCap projects and their data is managed by the owner of the project. All transactions are securely delivered to the application using Secure Sockets Layer (SSL – SHA-1 with RSA Encryption; 2048-bits). It is then transmitted internally

(behind the firewall) to the database server. All transactions are logged at the server layer (httpd logging), application layers (REDCap logs activity to a database table), and the database layer, using both query and binary logging. This feature provides audit trails for all changes, queries, data exports and reports. MUSC Information security policies are available at: <https://mainweb.v.musc.edu/security/policy/>

Data Entry. Only MUSC IRB approved study personnel that are authorized to have access to the REDCap study database will be granted password access. Study personnel using computers that are connected to the Internet will directly enter data into the remotely housed database. As such, no electronic study data will be stored on hard drives and/or any portable electronic devices. Additionally, all personnel with access to the database will have current University of Miami CITI and GCP training in the Conduct of Human Subject Protections, and HIPAA and Information Security trainings that are completed annually. Each participant will be assigned a unique study identifier, all PHIs will be masked, and data exports will be limited to the PI or the BS for generating reports and the conduct of statistical data analysis.

Data Monitoring. Ongoing quality control procedures will be implemented for data collection, storage and processing. The PI or PD will conduct monitoring of the study database and generate a report for review at team meetings. Standing agenda items for these meetings will include participant recruitment and retention, AE's, protocol deviations, data integrity and overall study conduct. The PI and PD will work to resolve and validate discrepant data. Discrepancies that warrant clarification will be sent to appropriate parties for review and resolution. All data entry and changes made in the study database by authorized study personnel will be automatically logged by REDCap, and provide a transparent visible audit trail for reviewers.

